**Table 7.11-1 Adverse Event Classification**

Type of AE	Reference Period for Baseline	Starting Point of Period	Ending Point
TEAE	Screening+ pretreatment	First dose during treatment period	Earlier of day after last dose of Trt period & day before first dose of RW period
RW TEAE	Screening+ pretreatment	First dose during RW period	Day after date of last dose of RW trt
NEAE	Screening+ pretreatment+ treatment	First dose during RW period	Day after date of last dose of RW trt

The number and percentage of patients in each treatment group who experience TEAEs will be summarized. For the Treatment Period, TEAEs will be summarized for each treatment group by system organ class and preferred term; by system organ class, preferred term, and severity; and by system organ class, preferred term, and relationship to study drug. The same summaries will be provided for each treatment sequence for the RW Period (RW TEAEs and NEAEs). For the Treatment-RW Period, TEAEs will be summarized for each treatment sequence by system organ class and preferred term only. If a patient has more than 1 AE coded to the same preferred term, the patient will be counted only once for that preferred term by identifying those TEAEs with the greatest severity and the closest relationship to study drug for the summarization by severity and by relationship to the study drug, respectively.

For the Treatment Period, the incidence of common ( $\geq 2\%$  of patients in any treatment group) TEAEs, on-therapy serious adverse events (SAEs), and AEs leading to premature discontinuation of study drug will be summarized by preferred term and treatment group, sorted in decreasing frequency. The above summaries will also be provided for the RW Period by treatment sequence. In addition, the incidence of on-therapy SAEs that led to death will be summarized.

For the Screened Population, listings will be presented for patients who died, patients with SAEs, and patients with AEs leading to premature discontinuation, if any.

### 7.11.2 Clinical Laboratory Parameters

Descriptive statistics for clinical laboratory values (in SI units) and changes from the baseline values at each assessment time point will be presented by treatment group for Treatment Period and by treatment sequence for the RW Period. The End of Treatment is the last non-missing postbaseline value in the Treatment Period; End of study is the last non-missing postbaseline value. The hematology and chemistry laboratory parameters listed in Section 5.4.5 will be summarized.

Clinical laboratory test values will be potentially clinically significant (PCS) if they meet either the low or high PCS criteria listed in Table 7.11-2. The number and percentage of patients with postbaseline PCS clinical laboratory values will be tabulated by treatment group for the Treatment Period and by treatment sequence for the RW and Treatment-RW Periods. The percentages will be calculated relative to the number of patients with non-PCS baseline values and at least 1 assessment in the corresponding postbaseline period. A supportive listing of patients with postbaseline PCS values will be provided, including the PID number, trial center, and baseline and postbaseline values. A listing of all AEs for patients with PCS clinical laboratory values will also be provided. The PCS flags will be derived flags (not from the clinically significant laboratory tests reported as AEs by trial centers).

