**Safety Measures:**

AE recording (each visit), clinical laboratory measures (chemistry and hematology: Screening, Randomization, Week 12/ETP, and Week 16/EOT Visits), body weight (each visit), vital sign parameters (each visit).

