### **6.3 DISCONTINUATION OF PATIENTS FROM THERAPY OR ASSESSMENT**

A premature discontinuation will occur when a patient who signed the ICF ceases participation in the trial, regardless of circumstances, before the completion of the protocol. Patients can prematurely discontinue or be prematurely discontinued by the investigator or Sponsor from the trial at any time for any reason including the following:

- Failure to meet Inclusion/Exclusion Criteria (Screening or Pretreatment Failure)
- Adverse event (AE)
- Lack of efficacy
- Protocol violation
- Non-compliance with study drug
- Withdrawal of consent
- Lost to follow-up (every effort must be made to contact the patient; a certified letter must be sent)
- Trial termination by Sponsor
- Pregnancy
- Other, such as administrative reasons

Patients who are randomized but do not complete the Treatment Period or RW Period (withdraw consent or are discontinued before they have completed 12 weeks or 4 weeks of treatment, respectively) will be considered Treatment Period or RW Period withdrawals, respectively, and should complete the procedures required at the Week 16/EOT Visit (even if out of window) at the time of their discontinuation. The reasons for premature discontinuation from the trial will be documented on the study termination form of the eCRF. All data on the patient prior to discontinuation will be made available to Ironwood (or designee). Any patient who withdraws because of an AE will be followed until the AE resolves, stabilizes, or can be explained as being unrelated to study drug. The trial centers should make a reasonable effort to follow pregnant patients until delivery or end of the pregnancy.

If a patient does not return for a scheduled termination visit (EOT Visit), the trial center should contact the patient. Every effort is to be made to contact the patient, including sending a certified letter. In every case, the patient outcome, including lost to follow-up information, will be documented.

The investigator may allow a patient to stop taking study drug for up to 3 days should an intolerable AE occur. If the investigator believes that the patient is unable to resume dosing or requires a suspension of dosing on more than one occasion, the investigator should contact the Medical Monitor to discuss the patient's continued participation in the trial.

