#### **10.6.2 Clinical Laboratory Parameters**

Descriptive statistics for clinical laboratory values (in standard units) and changes from the baseline values at each assessment time point will be presented by treatment group for the Treatment Period and by treatment sequence for the Combined Treatment and RW Period, for each clinical laboratory parameter.

The number and percentage of patients with potentially clinically significant (PCS) post-baseline clinical laboratory values will be tabulated by treatment group for the Treatment Period and by treatment sequence for the RW Period and the Combined Treatment and RW Period. The criteria for PCS laboratory values will be detailed in the SAP. The percentages will be calculated relative to the number of patients with available non-PCS baseline values and at least 1 assessment in the corresponding post-baseline period. The numerator will be the total number of patients with available non-PCS baseline values and at least 1 PCS value in the corresponding post-baseline period. A supportive listing of patients with PCS post-baseline values will be provided, including the PID number, trial center, and baseline and post-baseline values. A listing of all AEs for patients with PCS laboratory values will also be provided.

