#### Randomized Withdrawal Safety Population

The RW Safety Population consists of all patients who were re-randomized to or assigned to double-blind RW treatment and received at least one dose of RW treatment.

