## **9.5 REPEATED OR UNSCHEDULED ASSESSMENTS OF SAFETY PARAMETERS**

If a patient has repeated assessments prior to the start of double-blind study drug, then the results from the final non-missing assessment made prior to the start of the double-blind study drug will be used as baseline. If end-of-trial assessments are repeated or if unscheduled visits occur, the last non-missing post baseline assessment will be used as the end-of-trial assessment for generating summary statistics. However, all post-baseline assessments will be used for PCS value determination as described above and all assessments will be presented in the data listings.

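### SAP 7.11.2 sets no period limit on the End of study laboratory value, so a pre-re-randomization Week 12 sample can enter the RW Period row; and Table 9.1-1 leaves open Week 4 and Week 8 laboratory rows with no scheduled samples

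*SAP*

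**What the plan says.** **End of study.** SAP Section 7.11.2 says that laboratory descriptive statistics "will be presented by treatment group for Treatment Period and by treatment sequence for the RW Period". Protocol Section 10.6.2 planned them "by treatment group for the Treatment Period and by treatment sequence for the Combined Treatment and RW Period". The SAP then defines the two end-of-period values: "The End of Treatment is the last non-missing postbaseline value in the Treatment Period; End of study is the last non-missing postbaseline value". Section 9.5 repeats the second rule for repeat and unscheduled samples: "the last non-missing post baseline assessment will be used as the end-of-trial assessment for generating summary statistics".

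Under SAP Section 7.11, RW and combined-period safety analyses use the RW Safety Population. Membership requires that the patient was re-randomized or assigned to RW treatment and "received at least one dose of RW treatment"; no RW laboratory sample is required.

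**Visit windows.** The protocol synopsis schedules "clinical laboratory measures (chemistry and hematology: Screening, Randomization, Week 12/ETP, and Week 16/EOT Visits". SAP Table 9.1-1 assigns visits for the safety analysis as a whole: Days 2 to 43 are Week 4, Days 44 to 71 are Week 8, and Day 72 up to RW Day 1 is Week 12. Patients who withdraw early "should complete the procedures required at the Week 16/EOT Visit (even if out of window) at the time of their discontinuation", and those procedures include laboratory tests.

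**The concern.** The SAP limits End of Treatment to its period but does not limit End of study, and it puts that value beside an RW Period display. Applied literally, the rule fills the RW row with a Treatment Period value whenever a dosed RW patient has no RW sample. In a sequence that switches treatment, the value then reflects the treatment before the switch while carrying the label of the treatment after it. The protocol gives detecting withdrawal effects as a purpose of the RW Period, so diluting a switch effect works against that aim, even in a descriptive table.

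The windows raise a second, conditional question. If laboratory rows were printed at Week 4 and Week 8, they would look like scheduled visits but hold only patients who stopped early or had a repeat or extra test. An arm-level reading of such a row would compare selected patients.

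**Working it through.** The plan gives no figure on this point to reproduce. Its power figures do not bear on a descriptive laboratory table.

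**1. Which value the End of study rule returns**

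The schedule of evaluations marks the Week 12 laboratory sample as taken before randomization. Protocol Section 7.5 has the patient take the usual Treatment Period dose that morning and the first RW dose the next day. The Week 12 sample therefore always reflects Treatment Period drug.

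| Sequence | RW sample exists | No RW sample | Drug behind the substituted value |
|---|---|---|---|
| 290-290 | RW value | Week 12 value | linaclotide, same as in RW |
| 290-Placebo | RW value | Week 12 value | linaclotide, not the RW placebo |
| Placebo-290 | RW value | Week 12 value | placebo, not the RW linaclotide |

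The rule is correct whenever an RW sample exists. It misattributes treatment only in the last column of the two switching sequences. In 290-290 the value is early but on the same drug.

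**2. How many patients (illustration)**

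From the documents: 300 patients per arm, with linaclotide patients re-randomized 1:1. Assumed, because the documents give no rate: a fraction c = 0.75 to 0.95 of each arm enters RW, and a fraction m = 0.02 to 0.10 of those have no RW sample.

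- 290-Placebo: n = 300 × c / 2 = 112.5 to 142.5. Affected = n × m, from 112.5 × 0.02 = 2.25 to 142.5 × 0.10 = 14.25.
- Placebo-290: n = 300 × c = 225 to 285. Affected = from 225 × 0.02 = 4.5 to 285 × 0.10 = 28.5.

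If patients without an RW sample would have shifted like the others, a true mean shift d on switching appears in the row as (1 − m) × d. On these assumptions it is diluted by 2% to 10%.

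**3. What is not touched**

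SAP Section 7.11.2 bases PCS percentages on patients with at least one assessment in the corresponding postbaseline period, so they do not depend on the End of study rule. Efficacy uses diary data.

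**4. Scheduled samples passed through Table 9.1-1**

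- Randomization, Day 1: Baseline.
- Week 12 visit, Day 85 ± 3, so Days 82 to 88: Week 12.
- Scheduled laboratory samples on Days 2 to 71: none.

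Samples that can fall on those days are early-withdrawal samples, repeats of clinically significant abnormal results, and additional tests, which Protocol Section 8.2.2 allows at any time. Withdrawal samples on Days 2 to 43 map to Week 4, those on Days 44 to 71 to Week 8, and later ones to Week 12.

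Illustration, all rates assumed: with 5% to 25% withdrawing, 60% to 90% of them on Days 2 to 71, and 50% to 100% of those giving a sample, the two rows together would hold from 300 × 0.05 × 0.6 × 0.5 = 4.5 to 300 × 0.25 × 0.9 × 1.0 = 67.5 withdrawal samples per arm.

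**The case against.** **On End of study.** The SAP also plans safety analyses for the combined 16-week period, where an unrestricted last value is an ordinary definition and correctly labelled. In an RW-only table a programmer might restrict it without being told. RW withdrawals are asked to give end-of-trial samples, and sites must pursue patients who do not return, so few should lack one. The point about numbers stands. The point about reading does not remove the problem: Section 7.11.2 names the RW Period, not the combined period, for laboratory means by sequence; the same sentence restricts one end value and not the other; and Section 9.5 repeats the unrestricted rule.

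**On the windows.** One shared table is needed because vital signs and weight are measured at Weeks 4 and 8. Section 7.11.2 refers to assessment time points for laboratory data, where 7.11.3 refers to visits for vital signs, so scheduled laboratory visits only is a fair reading. Section 9.5 routes unscheduled samples to the end-of-trial value, and table specifications are in a separate document. This stands, and it makes the second part conditional.

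**Stronger readings a reader might infer.**

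- That Table 9.1-1, footnote b, puts laboratory data at Weeks 4 and 8. The note belongs to the end-of-period row and says nothing about those weeks.
- That the Week 4 and Week 8 rows would show about 16 linaclotide against 1 placebo patient, from the earlier trials' diarrhea discontinuation rates (300 × 5.3% = 15.9; 300 × 0.4% = 1.2). The rows would hold withdrawals for any reason, plus repeat and extra tests, so that contrast does not describe them.
- That vital signs share the problem. Section 7.11.3 shows their means by sequence for the combined period, where a Week 12 value belongs.

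**Conclusion.** The End of study point holds as a defect of wording with a small practical effect. As written, the rule puts pre-re-randomization values in an RW Period row for patients dosed in RW who have no RW sample. It misattributes treatment in 290-Placebo and Placebo-290 only. About 2 to 14 and 5 to 29 patients, respectively, would be affected under the assumed rates; the true numbers are probably toward the low end, because end-of-trial samples are requested at withdrawal.

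The window point holds only conditionally. The mapping of Days 2 to 71 to Week 4 and Week 8 is explicit, but the documents do not establish that laboratory rows will be printed there. A reader should not conclude that they will.

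Safety is analysed descriptively, so no test, power or error rate is at stake. This is worth correcting because the remedy is simple, not because it threatens a conclusion of the trial.

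**What to change.** 1. In SAP Section 7.11.2, for RW Period laboratory displays, define End of study as the last non-missing value after the first RW dose, which matches the start Table 9.1-1 already sets for Week 16. Patients without such a value are left out of that row. Alternatively, restore the protocol's combined Treatment and RW display, where the existing definition fits. Add a matching cross-reference in Section 9.5.
2. State that by-visit laboratory rows are limited to Baseline, Week 12 and Week 16, plus the end-of-period rows. Early-withdrawal, repeat and unscheduled samples then enter through End of Treatment, the PCS tables and the listings.

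Section 7.11.3 needs no change. The cost is about two sentences. With the first option a few patients drop out of the RW End of study row; their Week 12 values remain in the Treatment Period summaries.

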**Table 7.11-2 Criteria for Potentially Clinically Significant Laboratory Results**

Parameter	SI Unit	Lower Limit	Higher Limit
CHEMISTRY			
Albumin	g/L	< 0.9 × LLN	> 1.1 × ULN
Alanine aminotransferase	U/L	—	≥ 3 × ULN
Alkaline phosphatase	U/L	—	≥ 3 × ULN
Aspartate aminotransferase	U/L	—	≥ 3 × ULN
Bicarbonate	mmol/L	< 0.9 × LLN	> 1.1 × ULN
Bilirubin, total	µmol/L	—	> 1.5 × ULN
Calcium	mmol/L	< 0.9 × LLN	> 1.1 × ULN
Chloride	mmol/L	< 0.9 × LLN	> 1.1 × ULN
Cholesterol, total	mmol/L	—	> 1.6 × ULN
Creatinine	µmol/L	—	> 1.3 × ULN
Glucose	mmol/L	< 0.8 × LLN	> 1.4 × ULN
Magnesium	mmol/L	< 0.9 × LLN	> 1.1 × ULN
Phosphate	mmol/L	< 0.9 × LLN	> 1.1 × ULN
Potassium	mmol/L	< 0.9 × LLN	> 1.1 × ULN
Protein, total	g/L	< 0.9 × LLN	> 1.1 × ULN
Sodium	mmol/L	< 0.9 × LLN	> 1.1 × ULN
Urea nitrogen	mmol/L	—	> 1.2 × ULN
Uric acid	µmol/L	< 0.9 × LLN	> 1.1 × ULN

Parameter	SI Unit	Lower Limit	Higher Limit
HEMATOLOGY			
Basophils, absolute cell count	10  /L	—	> 3 × ULN
Eosinophils, absolute cell count	10  /L	—	> 3 × ULN
Hematocrit	Ratio	< 0.9 × LLN	> 1.1 × ULN
Hemoglobin	g/L	< 0.9 × LLN	> 1.1 × ULN
Lymphocytes, absolute cell count	10  /L	< 0.8 × LLN	> 1.5 × ULN
Mean corpuscular hemoglobin	pg	—	> 3 × ULN
Mean corpuscular hemoglobin concentration	g/L	—	> 3 × ULN
Mean corpuscular volume	fL	< 0.9 × LLN	> 1.1 × ULN
Monocytes, absolute cell count	10  /L	—	> 3 × ULN
Neutrophils, absolute cell count	10  /L	< 0.8 × LLN	> 1.5 × ULN
Platelet count	10  /L	< 0.5 × LLN	> 1.5 × ULN
Red blood cell count	10  /L	< 0.9 × LLN	> 1.1 × ULN
White blood cell count	10  /L	< 0.7 × LLN	> 1.5 × ULN

LLN = lower limit of normal value provided by the laboratory; SI = *Le Système International d'Unités* (International System of Units); ULN = upper limit of normal value provided by the laboratory.

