#### **5.4.5        Clinical Laboratory Data**

Fasted blood and urine samples for clinical laboratory tests will be collected at the days and times defined in the Schedule of Evaluations ([Table 5.1-1](#)). A central laboratory will be used to evaluate all blood and urine samples (except the urine pregnancy test).

The following clinical laboratory tests will be performed:

**Hematology:** Absolute and differential white blood cell count, erythrocyte count, hemoglobin, hematocrit, platelet count, and red blood cell indices (mean corpuscular volume, mean corpuscular hemoglobin, and mean corpuscular hemoglobin concentration)

**Chemistry:** Sodium, magnesium, potassium, calcium, chloride, glucose, blood urea nitrogen, creatinine, total protein, alkaline phosphatase, albumin, total bilirubin, aspartate aminotransferase, alanine aminotransferase, bicarbonate, phosphate, cholesterol, and uric acid

**Other:** Urine drug screening (cocaine, barbiturates, amphetamines, opiates, benzodiazepine, alcohol, and cannabinoids) (Screening Visit only). Clinical significance of a positive urine drug screen will be assessed by the investigator; positive results for cocaine, barbiturates, and cannabinoids are exclusionary.

**Pregnancy test:** Serum human chorionic gonadotropin pregnancy test (for women of childbearing potential only) should be conducted at the Screening Visit and Week 16/EOT Visit. A negative urine pregnancy test must be documented at the Randomization Visit and the Week 12/ETP Visit for the patient to be eligible for randomization and dosing with study drug. Positive results on the pregnancy test will exclude a patient from participating or continuing in the trial.

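### The PCS limits for MCH and MCHC in SAP Table 7.11-2 (above 3 × ULN, no lower limit) cannot plausibly be met by a true value, so these two rows give no safety information

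*SAP*

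**What the plan says.** SAP section 5.4.5 lists the red cell indices measured in the trial: "mean corpuscular volume, mean corpuscular hemoglobin, and mean corpuscular hemoglobin concentration". Protocol section 10.6.2 leaves the PCS criteria to the SAP, and SAP section 7.11.2 gives the rule: "Clinical laboratory test values will be potentially clinically significant (PCS) if they meet either the low or high PCS criteria" in Table 7.11-2. It then states: "The number and percentage of patients with postbaseline PCS clinical laboratory values will be tabulated by treatment group". That tabulation covers the Treatment Period; the RW Period and the combined period are tabulated per sequence. The denominator is patients with a non-PCS baseline value and at least one assessment in the period.

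The relevant hematology rows of Table 7.11-2 are:

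| Parameter | Lower limit | Higher limit |
|---|---|---|
| MCH ("Mean corpuscular hemoglobin") | none | > 3 × ULN |
| MCHC ("Mean corpuscular hemoglobin concentration") | none | > 3 × ULN |
| Basophils, eosinophils, monocytes (absolute counts) | none | > 3 × ULN |
| Hemoglobin, hematocrit, red blood cell count, MCV ("Mean corpuscular volume") | < 0.9 × LLN | > 1.1 × ULN |

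No other part of the protocol or SAP gives MCH or MCHC a different criterion. The documents contain no numerical reference ranges; the table footnote says only "ULN = upper limit of normal value provided by the laboratory".

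**The concern.** MCH and MCHC share a rule that the hematology section otherwise uses only for three white-cell counts. Such counts can rise several-fold. A red cell index is a ratio of quantities that the same table treats as notable when they are 10% beyond the normal range, so it makes little sense to require a tripling before the ratio is flagged. With no lower limit, the upper limit is the only route to a flag. If it cannot be reached, the two rows have a fixed outcome.

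At stake is the meaning of a planned safety output. Nobody would be PCS at baseline either, so every patient with a baseline and a later assessment would enter the denominator, and the result would be 0 out of nearly everyone in each arm and period. That looks like an observation, but it follows from the criterion.

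**Working it through.** The plan states no figure here that could be reproduced. The check is whether 3 × ULN can be reached.

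**Inputs from the SAP.** The limits and units in Table 7.11-2: hemoglobin (Hb) in g/L, hematocrit (Hct) as a ratio, red blood cell count (RBC) in 10^12/L, MCV in fL, MCH in pg, MCHC in g/L.

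**Assumptions, not in the documents.** MCH ULN 31-35 pg; MCHC ULN 350-370 g/L; Hb ULN 150-180 g/L; Hct LLN 0.33-0.41; RBC LLN 3.6-4.5 × 10^12/L.

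**Definitions.** MCHC = Hb / Hct. MCH = Hb / RBC. MCH = MCHC × MCV / 1000.

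**Step 1: absolute cut-offs.**
- MCH: 3 × 31 = 93 pg to 3 × 35 = 105 pg.
- MCHC: 3 × 350 = 1050 g/L to 3 × 370 = 1110 g/L, which is more than 1 kg of hemoglobin per litre of packed red cells.

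**Step 2: components at the table's own limits.** Put Hb at 1.1 × ULN and the denominator at 0.9 × LLN in the same sample, a contrived combination that favours a high index.
- MCHC, lowest: (1.1 × 150) / (0.9 × 0.41) = 165 / 0.369 = 447 g/L. Highest: (1.1 × 180) / (0.9 × 0.33) = 198 / 0.297 = 667 g/L. The cut-off is 1050-1110 g/L.
- MCH, lowest: 165 / (0.9 × 4.5) = 165 / 4.05 = 41 pg. Highest: 198 / (0.9 × 3.6) = 198 / 3.24 = 61 pg. The cut-off is 93-105 pg.

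PCS limits flag values and do not bound them, so this is not a mathematical maximum. It shows that components already extreme enough to be flagged still leave both indices well short.

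**Step 3: MCV needed.** With MCHC at its ULN, an MCH of 3 × ULN needs MCV = 3 × MCH ULN × 1000 / MCHC ULN. This runs from 93 × 1000 / 370 = 251 fL to 105 × 1000 / 350 = 300 fL. The table already flags MCV at 1.1 × its ULN.

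**Step 4: distance in SDs.** Take the reference interval as mean ± 1.96 SD and let r = LLN/ULN. In units of ULN, the mean is (1 + r)/2 and the SD is (1 − r)/3.92.
- r = 0.70: (3 − 0.85) / 0.0765 = 28 SD above the mean.
- r = 0.95: (3 − 0.975) / 0.01276 = 159 SD above the mean.

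The expected number of true values above 3 × ULN in 300 patients is zero over this range.

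**Step 5: the related rows' limits for comparison.** The 1.1 × ULN cut-offs would be 34.1-38.5 pg (MCH) and 385-407 g/L (MCHC). For r from 0.75 to 0.90, the low limit lies 3.1 to 5.5 SD below the mean and the high limit 3.5 to 5.9 SD above it. These are extreme but attainable in abnormal blood, and low values could then be flagged.

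**The case against.** The best reply is that little depends on these rows. SAP section 7.11.2 also requires descriptive statistics and changes from baseline for every hematology parameter in section 5.4.5, so a shift in MCH or MCHC would show there. Hb, Hct, RBC and MCV have two-sided limits and should catch most relevant red-cell changes. Under Protocol sections 8.2.1.2.3 and 8.2.2, an abnormality that the investigator considers clinically significant is recorded as an AE whatever the derived flag says. All of this stands and keeps the point minor. It does not make the two rows informative, and means do not count individual patients, which is what a PCS tabulation is for.

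A reader might infer more than the documents support:
- *The count is zero whatever the data.* An analyser artefact, unit error or entry error could exceed 3 × ULN. The statement holds for true values only.
- *Red-cell changes will go unseen, or only low values matter clinically.* The summaries and related limits above answer the first. Nothing in either document supports the second.
- *A misleading 0% will be printed.* SAP section 1.0 puts table specifications in a separate document, so the display of parameters without events is unknown.
- *The limit was copied by mistake from the white-cell rows.* The shared rule is visible, but its origin is not.

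It can also be said that the documents do not establish 0.9 × LLN and 1.1 × ULN as the correct limits for these indices, since the table uses several multipliers. That is fair. The case for them is consistency with the related rows, and removing the two rows is an adequate alternative.

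**Conclusion.** The point holds, as a minor one. As written, the PCS criterion for MCH and MCHC has no low side and a high side that no true value can plausibly reach. Apart from artefact or data error, both will show zero PCS patients in every treatment group and sequence, and that zero says nothing about safety.

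The absolute cut-offs rest on assumed reference limits. The conclusion does not depend on their exact values: it held over every range tried, and the smallest margin was 28 SD. No efficacy result, hypothesis test, analysis population or patient decision is affected.

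**What to change.** Before unblinding, do one of the following in SAP Table 7.11-2:

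1. Replace the limits in the MCH and MCHC rows (four cells) with < 0.9 × LLN and > 1.1 × ULN, as the table already has for hemoglobin, hematocrit, MCV and red blood cell count.
2. Remove MCH and MCHC from the PCS tabulation and keep their descriptive summaries.

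These are derived reporting flags, so neither option touches investigator review or AE recording.

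Option 1 brings some extra flags and listing lines, partly duplicating hemoglobin or MCV flags. Under the normal reference model of Step 4, one reading from each of 300 patients would give about 0.32 expected flags per index at LLN/ULN = 0.75 and 0.08 at 0.80, and fewer for narrower ranges. Patients with abnormal blood would add to that. Option 2 costs only the two rows.
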